5.11 Subject Replacement Strategy

Subjects that fail to undergo the trimodality treatment will be replaced.

5.12 Beginning and End of the Trial

The overall trial begins when the first subject signs the informed consent form. The trial ends when the last subject completes the last trial visit, discontinues from the trial or is lost to follow-up (i.e. the subject is unable to be contacted by the investigator).

We expect to enroll one patient per month. This means that study can be finished within 2.5 years from the time the first subject signs the Informed Consent Form (ICF) through the final contact.

5.13 Clinical Criteria for Early Trial Termination

Early trial termination will be the result of the criteria specified below:

1. Quality or quantity of data recording is inaccurate or incomplete
2. Poor adherence to the protocol and regulatory requirements
3. Incidence or severity of adverse drug reaction in this or other studies indicates a potential health hazard to subjects

6.0 TRIAL FLOW CHART

6.1 Study Flow Chart

Trial period	Screening Phase	Imaging	Induction treatment phase	Surgery	Follow-up
Scheduling Window (Days)	-30 to -1	-14 to 0	From day 1 to day 56 (2 weeks after 2 nd pembrolizumab cycle)	From day 56 to day 70	From surgery to 6 months thereafter
Administrative Procedures					
Informed Consent	X				
Eligibility Criteria	X				
Demographics and Medical History	X				
Prior and Concomitant Medication Review	X				
PET Imaging					
⁸⁹ Zr-pembrolizumab		X ^a			
Clinical Procedures/Assessments					
Review Adverse Events	X		X ^b		
Full Physical Examination	X				
Directed Physical Examination	X		X ^b		X ^c
Vital Signs and Weight	X		X ^b		
ECOG Performance Status	X		X ^b		
12-lead ECG	X				
¹⁸ F-FDG PET-CT		X		X	
Laboratory Procedures/Assessments					
Pregnancy Test	X				
Complete Blood Count (CBC)	X	X ⁱ	X ^b		
Comprehensive Serum Chemistry Panel	X		X ^b		
Urinalysis	X				
T3, FT4 and TSH	X		X ^d		
Treatment					
SBRT			X		
Pembrolizumab			X ^a		
Surgery				X	
Efficacy Measurements					
Tumor Imaging (CT thorax +/- abdomen and MRI brain)		X	X ^e		X ^f
Tumor Tissue and Blood analysis					
Core tumor biopsy	X				
EBUS FACS		X	X ^g		
Surgical resection specimen				X	
Immunophenotyping		X ^h	X ^h	X ^h	X ^h

X^a: only for patients randomized to the SBRT + pembrolizumab arm; X^b: every cycle; every 6 weeks; X^c: if indicated; X^d: after 2nd pembrolizumab cycle; X^e: within 2 weeks of surgery; X^f: following resection every 3 months for the first 2 years and every 6 months for the 3 years thereafter; X^g:; X^g:between week 2 and 3 after SBRT; . X^h: see section 7.1.2.10 for timepoints; Xⁱ: 72 and 144 hours post-injection for patients undergoing ¹⁸F-FGD-PET-CT

7.0 TRIAL PROCEDURES

7.1 Trial Procedures

The Trial Flow Chart - Section 6.0 summarizes the trial procedures to be performed at each visit. Individual trial procedures are described in detail below. It may be necessary to perform these procedures at unscheduled time points if deemed clinically necessary by the investigator.

Furthermore, additional evaluations/testing may be deemed necessary for reasons related to subject safety. In some cases, such evaluation/testing may be potentially sensitive in nature (e.g., HIV, Hepatitis C, etc.), and thus local regulations may require that additional informed consent be obtained from the subject. In these cases, such evaluations/testing will be performed in accordance with those regulations.

7.1.1 Administrative Procedures

7.1.1.1 Informed Consent

The Investigator must obtain documented consent from each potential subject prior to participating in a clinical trial.

7.1.1.1.1 General Informed Consent

Consent must be documented by the subject's dated signature or by the subject's legally acceptable representative's dated signature on a consent form along with the dated signature of the person conducting the consent discussion.

A copy of the signed and dated consent form should be given to the subject before participation in the trial.

The initial informed consent form, any subsequent revised written informed consent form and any written information provided to the subject must receive the IRB/ERC's approval/favorable opinion in advance of use. The subject or his/her legally acceptable representative should be informed in a timely manner if new information becomes available that may be relevant to the subject's willingness to continue participation in the trial. The communication of this information will be provided and documented via a revised consent form or addendum to the original consent form that captures the subject's dated signature or by the subject's legally acceptable representative's dated signature.

Specifics about a trial and the trial population will be added to the consent form template at the protocol level.

The informed consent will adhere to IRB/ERC requirements and applicable laws and regulations.

7.1.1.2 Inclusion/Exclusion Criteria

All inclusion and exclusion criteria will be reviewed by the investigator or qualified designee to ensure that the subject qualifies for the trial.

7.1.1.3 Medical History

A medical history will be obtained by the investigator or qualified designee. Medical history will include all active conditions, and any condition diagnosed within the prior 10 years that are considered to be clinically significant by the Investigator.

7.1.1.4 Prior and Concomitant Medications Review

7.1.1.4.1 Prior Medications

The investigator or qualified designee will review prior medication use, including any protocol-specified washout requirement, and record prior medication taken by the subject within 28 days before starting the trial.

7.1.1.4.2 Concomitant Medications

The investigator or qualified designee will record medication, if any, taken by the subject during the trial. All medications related to reportable SAEs and ECIs should be recorded as defined in Section 7.2.

7.1.1.5 Disease Details and Treatments

7.1.1.5.1 Disease Details

The investigator or qualified designee will obtain prior and current details regarding disease status.

7.1.1.5.2 Prior Treatment Details

The investigator or qualified designee will review all prior cancer treatments including systemic treatments, radiation and surgeries.

7.1.1.5.3 Subsequent Anti-Cancer Therapy Status

If a subject initiates a new anti-cancer therapy within 30 days after the last dose of trial treatment, the 30 day Safety Follow-up visit must occur before the first dose of the new therapy.

7.1.1.6 Assignment of Screening Number

All consented subjects will be given a unique screening number that will be used to identify the subject for all procedures that occur prior to the PET scans and pembrolizumab treatment. The screening assignment will start with the term PembroRTSurgery followed by the number of inclusion (e.g. PembroRTSurgery001).

7.1.1.7 Randomization

Patients will be randomized 1:1 by an automated program.

7.1.2 Clinical Procedures/Assessments

7.1.2.1 Adverse Event (AE) Monitoring

The investigator or qualified designee will assess each subject to evaluate for potential new or worsening AEs as specified in the Trial Flow Chart and more frequently if clinically indicated. Adverse experiences will be graded and recorded throughout the study according to NCI CTCAE Version 4.0. Toxicities will be characterized in terms regarding seriousness, causality, toxicity grading, and action taken with regard to trial treatment.

All AEs of unknown etiology associated with pembrolizumab exposure should be evaluated to determine if it is possibly an event of clinical interest (ECI) of a potentially immunologic etiology (irAE). See Section 5.8.1 regarding the identification, evaluation and management of AEs of a potential immunological etiology.

Detailed information regarding the assessment and recording of AEs can be found in section 7.2.

7.1.2.2 Full Physical Exam

The investigator or qualified designee will perform a complete physical exam during the screening period. Clinically significant abnormal findings should be recorded as medical history.

7.1.2.3 Directed Physical Exam

For cycles that do not require a full physical exam per the Trial Flow Chart, the investigator or qualified designee will perform a directed physical exam as clinically indicated prior to trial treatment administration.

7.1.2.4 Vital Signs

The investigator or qualified designee will take vital signs at screening, prior to the administration of each dose of trial treatment and at treatment discontinuation as specified in the Trial Flow Chart (Section 6.0). Vital signs should include temperature, pulse, respiratory rate, weight and blood pressure. Height will be measured at screening only.

7.1.2.5 Eastern Cooperative Oncology Group (ECOG) Performance Scale

The investigator or qualified designee will assess ECOG status at screening, prior to the administration of each dose of trial treatment and discontinuation of trial treatment as specified in the Trial Flow Chart.

7.1.2.6 Tumor Imaging and Assessment of Disease

Besides the baseline CT, ¹⁸F-FDG PET and ⁸⁹Zr-pembrolizumab PET imaging (described in section 5.3), the diagnostic CT chest will be repeated within two weeks before surgical resection (described in section 5.4). Follow-up following resection will be done with a diagnostic CT chest every 3 months for the first 2 years and every 6 months for the 3 years thereafter, according to institutional standards.

7.1.2.7 Tumor Tissue Collection

7.1.2.7.1 Pretreatment tumor biopsy

Tumor tissue for biomarker analysis from a newly obtained formalin fixed biopsy of the tumor must be provided in the form of a tissue block or at least ten unstained slides. A fine needle aspirate or cytologic specimen will not be acceptable. Needle or excisional biopsies are required. IHC analyses will include PD-1, PD-L1, CD4, CD8 and FoxP3, combined with Ki67 double staining to ascertain effector T cell activation and proliferation in the tumor microenvironment as reported by Tumeh et al. (Nature 2014), also taking into account the effect of quantitative IHC.

7.1.2.7.2 Post-resection specimen

Primary tumor

After resection, the resection specimen will be marked intraoperatively by the surgeon. To enable PET and pathology correlation, the resected specimen and the PET/CT scan are carefully inspected and tissue samples analyzed from the appropriate area of the specimen, according to institutional protocol (75). Margins of specimens will be inked, formalin fixed and sectioned into approximately 1 cm thick slices. Photographs of serial sections will be made. Subsequently, several tissue blocks will be sampled and embedded in paraffin. This facilitates orientation and localization of anatomical structures corresponding to different parts of the tumor on the PET/CT scans. Histological sections of the formalin fixed paraffin embedded blocks from the resected specimens will be examined blinded for the PET data. An estimation of the visually assessed vital tumor percentage will be given for the whole of the tumor. Multiple slides taken from all tumor segments (approximately 1 cm² each) will be scored by the same IHC panel as for the baseline biopsy, which is then used for comparison with SUV values. The presence of tumor cells that may influence the uptake of FDG will also be determined. All IHC parameters will be scored semi-quantitatively (absent = 0, few = 1, moderate = 2, extensive = 3). Tumor segment areas were evaluated per 1 cm², as this approximates the PET resolution and the dimension of the spherical ROI used to determine SUV_{peak}.

Lymph nodes

Immune cells will be isolated from the hilar and mediastinal lymph nodes in the resection specimen by the use of a cytologic scraping method as previously described (60). In short, lymph nodes will be bisected lengthwise with a surgical scalpel. From one half, 10 scrapes are made with a surgical blade (no. 22). The scrape material will be phenotypically analyzed by flow cytometry as described in section 5.5.2.

Tumor surrounding normal lobar lung tissue

The tumor surrounding non-tumor lobar lung tissue will be examined for radiation induced (fibrotic) changes. The percentage of fibrosis and immune cell infiltrate surrounding the tumor will be assessed semi-quantitatively (absent = 0, few = 1, moderate = 2, extensive = 3) (75).

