8.2.1 Tumor tissue

IHC analyses will be done on the pretreatment tumor biopsy and postinduction resection specimen of the primary tumor. The analyses include PD-1, PD-L1, CD4, CD8, FoxP3 and Ki67. Values will be quantified semi-quantitatively and compared within each patient (postinduction vs baseline) and between the treatment arms (SBRT vs SBRT + pembrolizumab) with the use of the Wilcoxon signed ranks test and the Wilcoxon-Mann Whitney test, respectively.

Immune cells will be isolated from the hilar and mediastinal lymph nodes in the resection specimen by the use of a cytologic scraping method as described in section 7.1.2.7.2. Values will be quantified on a linear scale and compared between the treatment arms (SBRT vs SBRT + pembrolizumab) with the use of the independent samples t-test.

The tumor surrounding non-tumor lobar lung tissue will be examined for radiation induced (fibrotic) changes. The percentage of fibrosis and immune cell infiltrate surrounding the tumor will be assessed semi-quantitatively and compared between the treatment arms (SBRT vs SBRT + pembrolizumab) with the use of the Wilcoxon-Mann Whitney test.

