9.3 Clinical Supplies Disclosure

This trial is open-label; therefore, the subject, the trial site personnel, the Sponsor and/or designee are not blinded to treatment. Drug identity (name, strength) is included in the label text; random code/disclosure envelopes or lists are not provided.

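### Masking to treatment arm is not stated for the visual 0-3 histology scores that are compared between arms in this open-label trial

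*Combined protocol and SAP*

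**What the plan says.** **Masking.** Section 7.1.2.7.2, under the primary tumor, has the only masking statement for tissue reading: "Histological sections of the formalin fixed paraffin embedded blocks from the resected specimens will be examined blinded for the PET data". The paragraph on normal lung tissue in the same section has no masking statement. Section 9.3 states: "This trial is open-label; therefore, the subject, the trial site personnel, the Sponsor and/or designee are not blinded to treatment". It makes no exception for pathology readers, and I found no section that masks any reader to arm.

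**Scale.** For the tumor, Section 7.1.2.7.2 says "All IHC parameters will be scored semi-quantitatively (absent = 0, few = 1, moderate = 2, extensive = 3"). For the surrounding lung it says "The percentage of fibrosis and immune cell infiltrate surrounding the tumor will be assessed semi-quantitatively (absent = 0, few = 1, moderate = 2, extensive = 3").

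**Analysis.** Section 8.2.1 on the tumor markers: "Values will be quantified semi-quantitatively and compared within each patient (postinduction vs baseline) and between the treatment arms (SBRT vs SBRT + pembrolizumab"), using the Wilcoxon signed ranks and Wilcoxon-Mann-Whitney tests respectively. On the lung: "The percentage of fibrosis and immune cell infiltrate surrounding the tumor will be assessed semi-quantitatively and compared between the treatment arms", again by Wilcoxon-Mann-Whitney.

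**Objectives and size.** The tumor markers belong to primary objective 2 (Section 3.1), whose hypothesis expects a larger immune response with the combination. Radiation change in healthy lung is exploratory objective 1 (Section 3.3), which has no hypothesis. Section 5.2 plans 10 patients per arm, without a formal power calculation.

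**The concern.** Choosing between few and moderate on a stained section is a judgment. When the reader knows the arm and the protocol says which arm should respond more, borderline cases can drift in that direction. With 10 patients per arm, a handful of shifted grades changes the comparison.

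The plan masks readers for the PET correlation, which is secondary (Sections 3.2 and 4.2.4), but states no such protection for the between-arm tumor comparison, which is part of a primary objective. It also mentions no second reader and no agreement check that could reveal drift.

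Sections 4.2.1 and 4.2.3 present the results as a proof of principle that comes before larger outcome studies. A difference produced by the reader would carry into those decisions. Later analysis could not remove it; the slides would have to be read again under masking.

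**Working it through.** The plan gives no figure to reproduce here: no significance level, effect size, SD or expected score distribution. The check therefore has two parts.

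**1. The sections side by side**

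| Scored item | Scale | Compared between arms | Masked to PET | Masked to arm |
|---|---|---|---|---|
| Tumor IHC: PD-1, PD-L1, CD4, CD8, FoxP3, Ki67 | 0-3, visual | Yes (8.2.1) | Yes (7.1.2.7.2) | Not stated |
| Fibrosis and infiltrate around the tumor | 0-3, visual | Yes (8.2.1) | Not stated in its own paragraph | Not stated |

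**2. How much reader drift would matter (illustration)**

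From the documents: 10 patients per arm (5.2), a 0-3 scale (7.1.2.7.2), and the Wilcoxon-Mann-Whitney test (8.2.1).

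Assumed: two-sided 5% level; one score per patient; the same true distribution in both arms, 25/35/25/15% for grades 0/1/2/3; each combination-arm case graded one step too high with probability q, with grade 3 as the ceiling.

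The mean shift produced by the reader follows directly. Cases already at grade 3 (15%) cannot move up, so

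shift = q × (1 − 0.15) = 0.85q.

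The spread of the score is

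- mean = 0.35×1 + 0.25×2 + 0.15×3 = 1.30
- mean square = 0.35×1 + 0.25×4 + 0.15×9 = 2.70
- SD = √(2.70 − 1.30²) = √1.01 ≈ 1.0

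So q = 0.1 moves the mean by 0.085 grade, which is small against an SD of about 1. At q = 0.5 the shift is 0.425 grade, or about 0.4 SD.

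Simulated false-positive rate per marker (20,000 runs per setting, tie-corrected normal approximation):

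| Share upgraded, q | Mean shift (grades) | False positives |
|---|---|---|
| 0 | 0 | 4.5% |
| 0.1 | 0.085 | 4.7% |
| 0.2 | 0.170 | 5.6% |
| 0.3 | 0.255 | 7.1% |
| 0.4 | 0.340 | 9.9% |
| 0.5 | 0.425 | 14.1% |

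The simulation standard error is √(0.045×0.955/20,000) ≈ 0.15 percentage points in the first row and √(0.141×0.859/20,000) ≈ 0.25 in the last.

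Sensitivity to the assumed distribution, using four others (25/25/25/25, 15/35/35/15, 40/40/15/5 and 10/60/25/5%):

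| q | Range of false positives |
|---|---|
| 0 | 4.3-4.7% |
| 0.1 | 4.4-5.0% |
| 0.2 | 5.2-7.6% |
| 0.3 | 6.1-12.0% |
| 0.5 | 10.2-26.0% |

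At q = 0.5 nearly all false positives favor the combination arm. With no upgrading, as under effective masking to arm, the rate stays near or just below 5% at the planned sample size.

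**The case against.** The best defense is that the plan is silent, not wrong. Section 9.3 concerns drug supplies and labeling. It confirms the open label but does not describe how slides are read, and the pathologist may in practice never learn the arm. The trial is exploratory, and modest drift scarcely changes the error rate. All of this stands. It limits the point to a missing safeguard but does not remove it, because a plan followed as written gives no assurance of masking.

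Some stronger readings are tempting, and the documents do not support them.

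- **That readers are told the arm.** No section says so.
- **That PET-guided sampling reveals the arm.** The zirconium scan is "only for patients randomized to the SBRT + pembrolizumab arm" (Section 6.1), but the flow chart lists FDG PET-CT without an arm restriction, and Section 5.3.1 makes PET-CT part of standard staging. Section 7.1.2.7.2 refers to the PET/CT scan in general terms. PET mapping can therefore apply to every patient and does not by itself identify the arm.
- **That primary objective 2 as a whole rests on visual grades.** Blood, lymph-node aspirates and node scrapes are flow-cytometry values on a linear scale (Sections 8.2.1 to 8.2.3). Only the tumor tissue is graded 0-3, and nothing examined here shows a masking problem with flow-cytometry gating.
- **That expectation pushes every score upward.** Exploratory objective 1 states no direction, and Section 4.1.7 foresees no added toxicity from the combination. For the tumor, a switch from suppressive to activated content could imply lower FoxP3, so drift could differ by marker.

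**Conclusion.** The point holds as an omission. The documents state no masking to treatment arm for visual grades that are compared between arms in an open-label trial. It affects the tumor IHC part of primary objective 2, where a direction is stated, and the fibrosis and infiltrate scores of exploratory objective 1, where none is and where even PET masking is not stated.

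The omission itself is certain; the size of its effect is not. Under the assumed 25/35/25/15% distribution, false positives per marker go from about 4.5% with no upgrading to 4.7% at 10%, 7.1% at 30% and 14.1% at 50%. The upgrade shares, the score distribution, the 5% level and the single score per patient are all assumptions. The plan scores several slides per tumor, which the illustration does not model. The figures show when drift would start to matter, not that it will occur.

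**What to change.** In Section 7.1.2.7.2, extend the masking sentence along these lines: sections are coded, read in random order across the two arms, and scored blinded to treatment arm as well as PET data; the code is opened only after all scores are locked. State that this covers both the tumor IHC scores and the fibrosis and infiltrate scores in the surrounding lung.

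This is a free improvement. It needs slide coding and a short protocol change, with no extra reader, patient or procedure and no change to the sample size or tests. The open-label treatment does not prevent it.

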3.2 Secondary Objectives & Hypotheses

Objective 1:

To assess uptake (visual and quantitatively, expressed as SUV_{max} , SUV_{mean} and SUV_{peak}) of radiolabeled pembrolizumab (^{89}Zr -pembrolizumab) in the tumor and lymph nodes by use of PET.

Hypothesis 1:

^{89}Zr -pembrolizumab tumor uptake heterogeneity between patients is expected and can be visualized. We expect that the level of ^{89}Zr -Pembrolizumab uptake will be related to the immunohistological results (immune effector subsets with special interest to the expression of PD-1 and PD-L1) of the whole tumor as well as regional tumor areas.

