8.5 Correlation between PET data and Blood and Tissue markers

The correlation between the continuous variable SUV and the categorical variables tissue PD-1 and PD-L1 IHC will be assessed with the ANOVA test. The correlation between the continuous SUV and blood variables will be assessed with the paired t-test.

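### The regional SUV-IHC comparison uses several segments per tumor, but the only test given has no patient term, and the plan does not say how several nodes per patient are combined

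*Combined protocol and SAP*

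**What the plan says.** **Regional aim.** The secondary hypothesis in section 3.2 relates tracer uptake to the immunohistological results "of the whole tumor as well as regional tumor areas". Sections 4.2.3 and 4.2.4 repeat the aim of setting 3D PET against 3D histology.

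**Segments.** Under section 7.1.2.7.2, slides from every tumor segment "will be scored by the same IHC panel as for the baseline biopsy, which is then used for comparison with SUV values". Scores run from 0 to 3. The segment area of about 1 cm² was chosen to approximate the PET resolution and the region used for SUVpeak.

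**Test for SUV against IHC.** Section 8.5: "The correlation between the continuous variable SUV and the categorical variables tissue PD-1 and PD-L1 IHC will be assessed with the ANOVA test". No other method is given for this relation.

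**Nodes.** Section 7.1.2.7.2: "Immune cells will be isolated from the hilar and mediastinal lymph nodes in the resection specimen". Section 8.2.1 has these values "compared between the treatment arms (SBRT vs SBRT + pembrolizumab) with the use of the independent samples t-test". Section 8.2.3 uses a paired t-test and an independent samples t-test for the EBUS nodes.

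**Tumor IHC over time and between arms.** Section 8.2.1 compares these "with the use of the Wilcoxon signed ranks test and the Wilcoxon-Mann Whitney test, respectively".

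Section 8 does not state the unit of analysis, a rule for reducing segments or nodes to one value per patient, a model that allows for clustering, or a significance level.

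**The concern.** Segments of one tumor share a patient, as do nodes of one patient, so their values are likely to be correlated. A test that counts them as independent overstates the information in about 10 PET patients, or in 10 patients per arm. A regional PET-IHC association could then look convincing because a few patients are high on both measures, not because uptake follows the marker within a tumor. In the same way, a node difference between arms could reflect a few unusual patients.

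The two parts differ. For nodes, a valid reading of the plan exists (one mean per patient) but is not written down. In an open-label trial with immune response as a primary endpoint, that choice should not wait until the data are seen. For the regional question, the named test offers no satisfactory reading: one value per patient cannot answer it, and several values per patient break the ANOVA's assumption.

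**Working it through.** The plan states no alpha or error rate for these tests, so there is no figure of its own to reproduce. The 5% two-sided level below is a convention.

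**Inputs from the documents**
- 10 patients per arm (section 5.2).
- ⁸⁹Zr-pembrolizumab PET in the pembrolizumab arm only (section 6.1, footnote a), so about 10 PET patients.
- Four IHC score levels, 0 to 3 (section 7.1.2.7.2).

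**Assumptions, because the documents give no figure**
- Segments per tumor: 3 to 15.
- Nodes per patient, m: 2 to 6.
- Within-patient correlation (ICC): 0.1 to 0.7.

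**What pooling does to the apparent sample.** With all four score levels present, 10 segments each from 10 patients give the ANOVA 10 × 10 − 4 = 96 residual degrees of freedom. One value per patient gives 10 − 4 = 6.

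**Nodes, formula.** DEFF = 1 + (m − 1) × ICC, and actual alpha = 2 × [1 − Φ(1.96 / √DEFF)].
- m = 2, ICC 0.3: DEFF = 1.3; 1.96/√1.3 = 1.72; alpha 8.6%.
- m = 6, ICC 0.7: DEFF = 1 + 5 × 0.7 = 4.5; 1.96/√4.5 = 0.92; alpha 35.6%.

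**Nodes, simulation** (independent t-test, 10 vs 10 patients, no true difference, 20,000 runs):

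| ICC | 2 nodes, pooled | 4 nodes, pooled | 6 nodes, pooled |
|---|---|---|---|
| 0.1 | 6.2% | 8.4% | 10.7% |
| 0.3 | 8.6% | 16.0% | 21.7% |
| 0.5 | 11.0% | 22.2% | 31.1% |
| 0.7 | 14.1% | 27.7% | 36.8% |

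With one mean per patient, the rate is 4.7-5.4% in every scenario, including ICC 0.

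**Segments, simulation** (one-way ANOVA of SUV on a four-level score, 10 patients, no true link, 4,000 runs). Patient effects in SUV and in IHC are independent of each other, and segments are independent given the patient:

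| ICC of IHC / SUV | 3 segments | 5 | 9 | 15 |
|---|---|---|---|---|
| 0 / 0.5 | 5.3% | 4.9% | 4.5% | 5.6% |
| 0.1 / 0.1 | 5.1% | 5.0% | 6.1% | 6.1% |
| 0.3 / 0.3 | 5.6% | 7.2% | 8.9% | 13.0% |
| 0.5 / 0.5 | 8.7% | 12.0% | 19.8% | 31.0% |
| 0.7 / 0.7 | 15.2% | 23.2% | 39.4% | 52.4% |
| 0.5 / one tumor SUV repeated | 13.9% | 22.6% | 37.2% | 48.8% |

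Separate runs at ICC 0.3-0.7 in both variables gave about 7-19% with 4 segments and 10-41% with 10, and about 4-6% at ICC 0.1. With one segment value per patient the ANOVA gives 4.3-5.4%.

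**Check of the remedy.** In runs at ICC 0.3-0.7 with 4, 6 and 10 segments, a slope of SUV on the score centered at each patient's own mean rejected in 4.7-5.7%.

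**The case against.** A reader might infer that the plan enters every segment and node as an independent observation, so that its error rates are inflated. The documents do not support that. Nowhere do they say that values are pooled. Several features point to the patient as the unit: section 5.2 counts patients, sections 8.2.1 and 8.2.3 compare within each patient, and section 8.2.3 calculates values by node class. On one value per patient, the node and whole-tumor tests keep about 5%.

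Nor are ANOVA and the independent t-test the only tests for these data. Wilcoxon tests are named for tumor IHC and a paired t-test for EBUS nodes, though these also need one value, or one pair, per patient.

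Section 8.5 does not mention segments, and sections 5.3.2.6 and 8.3 define SUV by tumor, node or organ. One can fairly say that a regional analysis is missing, not that a pooled ANOVA was chosen. The percentages also rest on assumed counts and correlations. ANOVA inflation needs clustering in both SUV and IHC, and the trial is exploratory.

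All of this stands, and it limits the node part to a missing detail. It does not settle the regional part. Sections 3.2 and 7.1.2.7.2 commit to a regional comparison, and the only test on offer does not suit it.

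**Conclusion.** The point holds in conditional form. The plan sets out a regional SUV-IHC comparison and gives for it only a test without a patient term. If segments are pooled, type I error is about 7-19% with 4 segments and 10-41% with 10. That assumes an ICC of 0.3-0.7 in both SUV and IHC and a conventional 5% level. At ICC 0.1, or if IHC does not cluster by patient, inflation is slight or absent.

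For nodes, the rule for combining values is unstated. Pooling would give about 9-14% with 2 nodes and 22-37% with 6 over the same ICC range.

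These are consequences of a choice that the plan leaves open, not error rates of the plan as written. The matter should be corrected in the SAP. It touches a secondary hypothesis and the node comparisons of an exploratory trial.

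**What to change.** - **Section 8.5, whole-tumor question:** use one SUV and one IHC value per patient, and state how the IHC value is derived.
- **Section 8.5, regional question:** define how SUV is measured for a segment. Then fit a mixed model of segment SUV on IHC score with a random patient intercept. Split the score into the patient's mean and the deviation from that mean; the deviation term answers the regional question.
- **Sections 8.2.1 and 8.2.3:** state that the patient is the unit. Average nodes within patient and node class (TDLN, NTDLN) before any test. For biopsy against resection, and for tumor IHC between arms, average segments within patient.
- **Limitation to record:** a random patient intercept does not model extra correlation between neighboring segments. The simulations above do not include it either.

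The cost is a few sentences in the SAP and a standard model, with no new data or procedures. P-values will tend to be less favorable than those from a pooled analysis.
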